APPENDIX C Phlebotomy Volume by Visit

Low Risk Group (volumes are approximate)

Study Visit Day →	1	4	8	15	29	43	71	99	127	155	183	274	365
Hepatitis B, C ^a	4												
HIV ^a	5												5
CBC, platelets ^a	2	2		2		2							
Serum chemistry ^{a, c}	4	4		4		4							
PT(INR), PTT ^a	2					2							
Serum RVNA	10 ^a	10 ^b	10 ^b	10 ^b	10	10	10	10	10	10	10	10	10
Anti-SYN023 serum assay	5 ^a			5	5			5	5	5	5	5	5
SYN023 concentration	5 ^a	5 ^b	5 ^b	5 ^b	5	5		5					
Per visit phlebotomy volume	37	21	15	26	20	23	10	20	10	10	10	10	15
Cumulative phlebotomy volume	37	58	73	99	119	142	152	172	182	192	202	212	227

Normal Risk Group (volumes are approximate)

Study Visit Day →	1	4	8	15	29	43	71	99	127	155	183	274	365
Hepatitis B, C ^a	4												
HIV ^a	5												5
CBC, platelets ^a	2	2		2		2							
Serum chemistry ^{a, c}	4	4		4		4							
PT(INR), PTT ^a	2					2							
Serum RVNA ^a	10	10	10	10	10	10	10	10	10	10	10	10	10
Anti-SYN023 serum assay	5 ^a			5 ^b				5					
SYN023 concentration	5 ^a	5 ^b	5 ^b	5 ^b				5					
Per visit phlebotomy volume	37	21	15	26	10	18	10	20	10	10	10	10	15
Cumulative phlebotomy volume	37	58	73	99	109	127	137	157	167	177	187	197	212

APPENDIX D Listing of Procedures by Study Visit**LRG Group Study Day Procedure of Subject Evaluations****LRG Study Day 1 (Randomization Date, Baseline)****Before Study Drug administration**

Obtain informed consent

Verify eligibility by review of inclusion/exclusion criteria

Record medical history Including date of last immunization for tetanus

Conduct and record physical examination and vital signs

Perform Baseline EKG

Collect urine sample for:

Urine βHCG (females only) must be confirmed negative before randomization

Baseline Urinalysis

Blood for: Baseline Hepatitis B, C, HIV-1, 2,

Blood for Baseline PT (INR), PTT

Blood for Baseline serum chemistry: total bilirubin, AST, ALT, ALP, creatinine, blood urea nitrogen, sodium, potassium, chloride, bicarbonate, calcium and others if part of panel

Blood for Baseline hematology: CBC including differential and platelets

Blood for Baseline serum RVNA, SYN023 concentration and anti-SYN023 antibodies

Bite wound washing or irrigation if no wound present

Photographs of all wounds

Confirmation visit scheduling if required

Record concomitant medications

Randomization

Study Drug Administration

Study Drug injection to wound or muscle if no wound

Rabies Vaccination #1

After Study Drug Administration

Record AEs/SAEs and

Record Solicited AEs

Wound or Site of injection examination

LRG Study Day 4

Blood for hematology: CBC including differential and platelets

Blood for serum chemistry: total bilirubin, AST, ALT, ALP, creatinine, blood urea nitrogen, sodium, potassium, chloride, bicarbonate, calcium and others if part of panel

Blood for Serum RVNA, and SYN023 concentration

Interval history

Record solicited AEs

Vital signs, focused physical examination

Confirmation visit findings (bite time, animal capture, location animal specimens, immunization records etc.)

Record AEs/SAEs

Record concomitant medications

Wound or site of injection examination

Rabies vaccination #2

LRG Study Day 8

Blood for Serum RVNA and SYN023 concentration

Interval history,

Record solicited AEs

Vital signs, focused physical examination

Confirmation visit findings (bite time, animal capture, location animal specimens, immunization records etc.)

Record AEs/SAEs

Record concomitant medications

Wound or site of injection examination

Rabies vaccination #3

LRG Study Day 15

Blood for hematology: CBC including differential and platelets

Blood for serum chemistry: total bilirubin, AST, ALT, ALP, creatinine, blood urea nitrogen, sodium, potassium, chloride, bicarbonate, calcium and others if part of panel

Blood for Serum RVNA, SYN023 concentration and anti-SYN023 antibodies

Interval history

Focused physical examination

Record AEs/SAEs

Record concomitant medications

Wound or site of injection examination

Rabies vaccination #4

LRG Study Day 29 (Visit window \pm 2 days)

Interval history

Wound or site of injection examination

Focused physical examination

Blood for Serum RVNA, SYN023 concentration and anti-SYN023 antibodies

Record AEs/SAEs

Record concomitant medications

Rabies vaccination #5

LRG Study Day 43 (Visit window \pm 4 days)

Blood for hematology: CBC (including differential and platelets)

Blood for PT (INR), PTT

Blood for serum chemistry: total bilirubin, AST, ALT, ALP, creatinine, blood urea nitrogen, sodium, potassium, chloride, bicarbonate, calcium and others if part of panel

Blood for Serum RVNA, and SYN023 concentration

Interval history

Focused physical examination

Record AEs/SAEs

Record concomitant medications

LRG Study Day 99 (Visit window \pm 7 days)

Interval history

Focused physical examination

Blood for Serum RVNA

Record SAEs

Record concomitant medications

LRG Study Day 71, 127, 155, (Visit window \pm 7 days), 183, 274 (Visit window \pm 14 days)

Interval history

Focused physical examination

Blood for Serum RVNA, SYN023 concentration and anti-SYN023 antibodies

Record SAEs

Record concomitant medications

LRG Study Day 365 (Visit window \pm 14 days)

Blood for HIV-1, 2

Interval history

Focused physical examination

Blood for Serum RVNA and anti-SYN023 antibodies

Record SAEs

Record concomitant medications

NRG Group Study Day Procedure of Subject Evaluations

NRG Study Day 1 (Randomization Date, Baseline)

Before Study Drug administration

Obtain informed consent

Verify eligibility by review of inclusion/exclusion criteria

Record medical history including date of last immunization for tetanus

Conduct physical examination and vital signs

Perform EKG

Collect urine sample for:

βHCG (all females)

Baseline Urinalysis

Blood samples for baseline Hepatitis B, C, HIV-1, 2

Blood for baseline PT (INR), PTT

Blood for baseline serum chemistry: total bilirubin, AST, ALT, ALP, creatinine, blood urea nitrogen, sodium, potassium, chloride, bicarbonate, calcium and others if part of panel

Blood for baseline Hematology: CBC including differential and platelets

Blood for baseline Serum RVNA, Anti-SYN023 antibody assay, SYN023 concentration

Bite wound washing or irrigation

Photographs of all wounds

Schedule confirmation visit

Record concomitant medications

Randomization

Study Drug Administration

Study Drug Wound injection

Rabies Vaccination #1

After Study Drug Administration

AEs/SAEs

Record Solicited AEs

Wound or site of injection examination

NRG Study Day 4

Blood for hematology: CBC including differential and platelets

Blood for serum chemistry: total bilirubin, AST, ALT, ALP, creatinine, blood urea nitrogen, sodium, potassium, chloride, bicarbonate, calcium and others if part of panel

Blood for Serum RVNA SYN023 concentration

Vital signs

Interval history

Focused physical examination

Rabies vaccination #2

Confirmation visit

AEs/SAEs

Solicited AEs

Record concomitant medications

Wound or Site of injection examination

NRG Study Day 8

Vital signs

Interval history

Focused physical examination

Blood for Serum RVNA and SYN023 concentration

Confirmation visit

Rabies vaccination #3

AEs/SAEs and concomitant medications

Solicited AEs

Wound or Site of injection examination

NRG Study Day 15

Hematology: CBC including differential and platelets

Serum chemistry: total bilirubin, AST, ALT, ALP, creatinine, blood urea nitrogen, sodium, potassium, chloride, bicarbonate, calcium and others if part of panel

Interval history

Focused physical examination

Blood for Serum RVNA, Anti-SYN023 serum assay, SYN023 concentration

Rabies vaccination #4

AEs/SAEs

Record concomitant medications

Wound or Site of injection examination

NRG Study Day 29 (Visit window \pm 2 days)

Interval history

Focused physical examination

Blood for Serum RVNA

Record AEs/SAEs

Record concomitant medications

Wound or Site of injection examination

Rabies vaccination #5

NRG Study Day 43 (Visit window \pm 4 days)

Blood for Hematology: CBC including differential and platelets

Blood for Serum chemistry: total bilirubin, AST, ALT, ALP, creatinine, blood urea nitrogen, sodium, potassium, chloride, bicarbonate, calcium and others if part of panel

Blood for PT (INR), PTT

Interval history

Focused physical examination

Blood for Serum RVNA

Record AEs/SAEs

Record concomitant medications

NRG Study Day 71 (Visit window \pm 7 days)

Interval history

Focused physical examination

Blood for Serum RVNA

SAEs

Record concomitant medications

NRG Study Day 99 (Visit window \pm 7 days)

Interval history

Focused physical examination

Blood for Serum RVNA, Anti-SYN023 serum assay, SYN023 concentration

SAEs

Record concomitant medications

NRG Study Day 127, 155 (Visit window \pm 7 days), 183, 274 (Visit window \pm 14 days)

Interval history

Focused physical examination

Blood for Serum RVNA

SAEs

Record concomitant medications

NRG Study Day 365 (Visit window \pm 14 days)

Blood for HIV-1, 2

Blood for Serum RVNA

Interval history

Focused physical examination

SAEs

Record concomitant medications

PEP	post exposure prophylaxis
PK	Pharmacokinetics
PT	preferred term
RFFIT	rapid fluorescent foci inhibition test
RVNA	rabies virus neutralizing activity
SAP	statistical analysis plan
SD	standard deviation
SE	standard error
SOC	system organ class
TEAE	treatment-emergent adverse events
T _{max}	time till maximum concentration
t _{1/2}	half-life
ULN	upper limit of normal
V _d	volume of distribution
WHO	World Health Organization

1. Introduction

The purpose of this statistical analysis plan (SAP) is to describe the procedures and statistical methods that will be used to analyze, and report results for

- subjects enrolled under Protocol version 2.0 (21Feb2019) to the initial Low Risk Group (LRG) and
- subjects enrolled under a later version of the Protocol (including, but not exclusively, version 3.0 (15Jul2019) and version 4.0 (15Aug2019)) to any of the LRG and Normal Risk Group (NRG).

2. Objectives

2.1. Primary Objective

The primary objective is a composite endpoint with four elements:

- To demonstrate that the geometric mean rabies virus neutralizing activity (RVNA) concentration for SYN023 recipients is superior to the geometric mean RVNA concentration for human rabies immune globulin (HRIG) recipients on Study Day 8 AND
- To demonstrate that the Study Day 99 geometric mean RVNA concentration for SYN023 recipients is not inferior to the geometric mean RVNA concentration for HRIG recipients AND
- To demonstrate that the percentage of subjects with RVNA concentration ≥ 0.5 IU/mL on Study Day 99 in SYN023 recipients is not inferior to the percentage of recipients with RVNA concentration ≥ 0.5 IU/mL for HRIG AND
- There are no cases of probable or confirmed rabies in SYN023 recipients.

2.2. Secondary Objective(s)

- To demonstrate that the geometric mean RVNA concentration for SYN023 is superior to the geometric mean RVNA concentration for HRIG on Study Day 4.
- To demonstrate that the geometric mean RVNA AUEC₁₋₁₅ for SYN023 is superior to the geometric mean RVNA AUEC₁₋₁₅ for HRIG
- To describe the ratio of the geometric mean concentrations of RVNA at each time point in SYN023 recipients divided by the geometric mean concentrations of RVNA in HRIG recipients for LRG and NRG in the Per-protocol and As-treated Populations.
- To describe the percentage of RVNA concentration ≥ 0.5 IU/mL at each time point for SYN023 and HRIG recipients for LRG and NRG in the Per-protocol and As-treated Populations.
- To describe the pharmacokinetics of SYN023 using non-compartmental analysis. V_d , C_{max} , T_{max} , AUC_{1-t} , AUC_{1-inf} , $t_{1/2}$, Cl , and λ_z will be calculated when possible in the LRG and NRG Per-protocol and As-treated Populations.

- To evaluate presence and effects of anti-SYN023 antibodies (anti-CTB011, anti-CTB012).
- To evaluate the safety of SYN023 compared to HyperRab® S/D.
- To describe any effect of increasing BMI on SYN023 and RVNA concentrations.

3. Investigational Plan

3.1. Overall Study Design and Plan

This is a Phase 2b, double blinded, randomized study of SYN023 compared to HyperRab® S/D (a licensed HRIG) for post exposure prophylaxis (PEP) of patients who have been confirmed to have met all inclusion/exclusion criteria for their treatment group. The desired indication is the prevention of rabies as part of PEP. The trial will be conducted in at least two countries where rabies occurs. The trial will enroll sequentially two different risk substrata of World Health Organization (WHO) Category 3 rabies exposure.

Table 3.1-1 Exposure Characteristics of the Low Risk Group (LRG) and Normal Risk Group (NRG)

Exposure Type	LRG	NRG
Head and neck bite	-	+
Genitalia bite	-	+
Arms bite	-	+
Hands bite	-	+
Trunk bite	+	+
Legs bite	+	+
Ankles bite	+	+
Foot bite	+	+
Non-bite lick	+	+
Non-bite scratch	+	+
Non-bite bat contact	+	+
Non-bite mucous membrane	+	+

Schedules of study procedures can be found in Section 15.1.

3.1.1. Low Risk Group

The LRG is composed of subjects who meet the modified WHO Categories 3 protocol exposure criteria (Protocol Section 2.2.1). Inclusion is limited to bites to the foot, ankle, leg or trunk and licks to broken skin, scratches with, or to broken skin, unprotected bat exposure or mucous membrane contamination by saliva or neural tissue. These exposures represent a lower rabies risk exposure within WHO Categories 3 (Table 3.1-1). Bites to the head, neck or genitalia are excluded from LRG Initial Enrollment and General Enrollment.

3.1.2. Initial Enrollment in the LRG (20 Subjects)

Safety and RVNA data through Study Day 29 from the initial 20 subjects of the LRG will be reviewed by the data safety monitoring board (DSMB) to confirm safety and the achievement of adequate RVNA levels ≥ 0.5 IU/mL on Study Day 15 and 29 from standard, wound management, study drug administration and rabies vaccination before LRG general enrollment is permitted. Subjects excluded for cause by the Per-Protocol Adjudication Board will not be included in the RVNA Per-protocol Population but will be included in the As-treated Population. The initial 20 subjects in the LRG will be randomized on a 3:1 (SYN023 to HRIG) ratio. The size of the initial LRG enrollment is arbitrary. The initial LRG enrollment is not part of the sample size calculations for the primary objective.

3.1.3. Advancement from Initial Enrollment LRG to General Enrollment LRG

The DSMB will permit enrollment of the general LRG if safety from the As-treated Population and RVNA pharmacodynamic data from the Per-protocol Population through Study Day 29 from the initial LRG enrollment are found to be satisfactory by the DSMB.

3.1.4. General Enrollment LRG

The LRG general enrollment of an additional 60 subjects will consist of low risk WHO Category 3 exposures (Table 3.1-1). Subjects in general enrollment LRG will be allocated with a 1:1 randomization to either SYN023 or HRIG treatment arms. Bites to the head, neck or genitalia are not included in the LRG.

3.1.5. Advancement from LRG General Enrollment to the NRG

If Study Day 99 efficacy (RVNA geometric mean concentration (GMC) and RVNA ≥ 0.5 IU/mL) and safety LRG data from the initial and general LRG enrollment have been judged to be adequate by the DSMB and there are no cases of rabies in SYN023 recipients by Study Day 183 then randomization into the NRG will be permitted. It is presumed that a case of clinical rabies in the study population would become known to the DSMB promptly. Clinical rabies follow-up of the LRG will be made available to the DSMB through 6+ months on all patients for consideration of NRG commencement. The 12 months of LRG follow-up will not have ended when NRG enrollment starts.

3.1.6. Enrollment of the NRG

The NRG will consist of all WHO Category 3 exposure (Table 3.1-1). The NRG includes all rabies risks. It is powered to evaluate the primary and some secondary study objectives and to contribute to the pharmacokinetic and pharmacokinetic description of SYN023.

Subjects will be allocated with a 1:1 randomization to either SYN023 or HRIG treatment arms. Within the NRG group, bites to the head, neck or genitalia that have the highest rabies risk will be stratified for each treatment arm in a 1:1 ratio. The DSMB will review the progress of pharmacodynamic and safety data during the NRG study period to avoid unnecessary risk or expense.

3.1.7. Study Duration and Follow-up

The subjects will be followed for 365 days post receipt of study drug unless withdrawn from the trial. It is important to have follow-up information on all study enrollees for the full duration of the study. Every effort should be made to remain in contact with study subjects in at least six-week intervals to establish if the subject is in good health and to inquire about planned relocations. If health problems have occurred, a verbal or written account of the duration and character of the difficulties should be obtained. This is especially important in the last six months of the study when clinic visits are less frequent.

3.2. Study Endpoints

3.2.1. Efficacy Evaluations

Efficacy evaluations include:

- Clinical Efficacy Evaluations: a confirmed or probable case of rabies
- Pharmacodynamic Efficacy Evaluations: Serum RVNA

These are defined as the primary endpoints in Section 8.1.

3.2.2. Immunology Laboratory Evaluations

Immunology laboratory evaluations include:

Sample Type	Assay	Purpose of Assay
Serum	SYN023 concentration (CTB011 and CTB012)	Pharmacokinetics (PK) evaluations (Section 3.2.3)
Serum	RVNA by rapid fluorescent foci inhibition test (RFFIT)	Rabies neutralizing antibody concentration from study drug and vaccination, surrogate of protection
Serum	Anti-SYN023 antibodies (CTB011 and CTB012)	Effect on safety and efficacy analysis

The RFFIT results will be reported in a standardized concentration represented as international units (IU) per mL of serum (e.g., 0.5 IU/mL).

These are defined as the secondary endpoints in Section 8.2.

3.2.3. Pharmacokinetic Evaluations

For the LRG subjects, PK samples for SYN023 concentration (CTB011 and CTB012) will be obtained among all SYN023 recipients per assessment schedule (Section 15.1.1). Similarly, for the NRG subjects, PK samples will be obtained at selected timepoints per assessment schedule (Section 15.1.2). PK parameters (V_d , C_{max} , T_{max} , AUC_{1-t} , AUC_{1-inf} , $t_{1/2}$, Cl , and λ_z) will be calculated, when possible, for the presentation of PK activities (Section 10.3).

3.2.4. Virology Laboratory

Biting animal specimens when available from brain, skin or blood will be evaluated locally for rabies diagnosis (Section 8.1.1.4).

3.2.5. Safety Endpoints

3.3. Study Drugs

Subjects being enrolled to the study will be randomized to take either SYN023 or HRIG on Study Day 1. If a subject is enrolled under Protocol Amendment 2.0, rabies vaccinations will be administered on Study Days 1, 4, 8, and 15. If a subject is enrolled under a later version of the Protocol, vaccinations will be administrated on Study Days 1, 4, 8, 15 and 29. It is believed that there is unlikely any clinical difference in the different dosing schedules.

3.3.1. Human Rabies Immune Globulin (HyperRab® S/D)

There are two dosage forms of HRIG that may be used in the study, a presently available 150 IU/mL preparation and a newly available 300 IU/mL preparation. All stocks of 150 IU/mL HRIG (HyperRab®) should be used at a study site before the study site can switch to the 300 IU/mL preparation. Once a study site has switched to the 300 IU/mL preparation it cannot again use the 150 IU/mL.

The dose of HRIG (HyperRab®) 20 IU/kg should be calculated based on body weight. The dose for the 150 IU/mL potency preparation is 0.133 mL/kg. The dose for the 300 IU/mL potency is 0.0665 mL/kg.

The calculated dose should be administered into the wound whether in subcutaneous tissue or muscle. For example, a 70 kg person receiving the 150 IU/mL potency has a calculated dose of 9.31 mL. The entire calculated dose must be given. If the fluid volume of the injection needs to be increased to enable all sites to be injected the pharmacy may dilute the calculated dose with saline when the syringe is prepared. Doses up to 3 mL may be given in at a single injection site (Protocol Section 3.7.1). Care must be taken NOT to administer a rabies vaccine near the study drug administration site.

3.3.2. SYN023

After thorough wound sanitation, injections of the entire calculated dose of SYN023 should be administered into and around all the bite wounds. The dose of SYN023 should be calculated based on body weight: 0.3 mg/kg. For example, a 70 kg person has a calculated dose of 21 mg. The entire calculated dose should be given. Doses up to 3 mL may be given at a single injection site. Care must be taken NOT to administer a rabies vaccine near the study drug administration site.

3.4. Rabies Vaccine (RabAvert® or Rabipur®) Administration

Rabies Vaccine (RabAvert® or Rabipur®) must be administered in a different area from the study drug infiltration to reduce interference. The 1 mL dose of the chicken fibroblast rabies vaccine should be administered in deltoid muscle. If not possible, then vaccination may be administered

in the vastus lateralis (thigh) or rectus femoris (thigh). The rabies vaccine should be administered as soon as possible after dose constitution. Rabies vaccination should be administered within 75 minutes after study drug.

4. General Statistical Considerations

As it is unlikely that there is any clinical difference between the 4 and 5 dose regimens, summaries will be grouped by study group (LRG and NRG) regardless the difference in dosing schedules. In each summary where applicable, subjects will be grouped by treatment (actual study drug received). The two treatment groups for the study are SYN023 and HRIG.

Continuous data will be described using descriptive statistics (i.e. n , mean, standard deviation (SD), median, minimum, and maximum). Categorical data will be described using the subject count and percentage in each category. For the summary statistics of all numerical variables, unless otherwise specified, minimum and maximum will be displayed to the same level of precision as reported. Mean and median will be displayed to one level of precision greater than the data collected. SD/standard error (SE) will be displayed to two levels of precision greater than the data collected. P-values will be rounded to three decimal places. If a p-value is less than 0.001 it will be reported as “<0.001.” If a p-value is greater than 0.999 it will be reported as “>0.999.” Data will be displayed in all listings sorted by treatment group (actual study drug received).

Subjects will be identified in the listings by the subject identification number concatenated with the site number.

When count data is presented, the percentage will be suppressed when the count is zero to draw attention to the non-zero counts. Where applicable, a row denoted “Missing” will be included in count tabulations to account for dropouts and missing values. The denominator for all percentages will be the number of subjects in that treatment within the analysis set of interest, unless otherwise specified.

Unless otherwise specified,

- baseline will be defined as the last non-missing assessment prior to the first dose date (and time, if available on Study Day 1).
- Change from baseline is defined as: post-baseline value – baseline value.

The Study Day will be calculated as follows:

- If the assessment date occurs on or after the date of the first dose of study drug:
Study Day = assessment date – first dose date + 1.
- If the date of interest occurs before the date of the first dose of study drug:
Study Day = assessment date – first dose date
- There is no Study Day 0.

Missing data will not be imputed except for incomplete or partial dates of adverse events (AEs) and concomitant medications. Imputation rules for such will be described in the corresponding sections.

By timepoint summaries will be based on case report form (CRF) visits. For efficacy analyses, unscheduled results will not be considered but only be listed in by-subject listings. For safety analyses, unscheduled results will not be presented in by-timepoint summaries. However, it will be considered for overall post-treatment maximum or minimum values when reporting safety abnormalities.

All analyses will be conducted using SAS Version 9.4 or higher. If not pre-specified, statistical tests will be two-sided and interpreted at a 5% significance level.

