Immunogenicity will be summarized for initial LRG subjects, general LRG subjects and NRG subjects, separately. The summary will take forms of GMC or GMT and be based on standard log transformations (Section 15.2) for all time points as collected and as available. If the assay read-out does not occur at the starting dilution – indicating a very low amount of antibodies, below the detection limit of the assay – then the antibody titer for the sample is set to D/2, half of the starting dilution. No imputation for missing data will be performed. Data will be transformed as appropriate prior to analysis. GM, Geo SD and 95% CI will be provided in summary tables. Inferential testing will not be performed. In case of pre-vaccination immunogenicity levels are not zero, GM fold increase will be presented as the alternative statistics to GMC or GMT. Let v_{pre} be a subject's pre-vaccination (baseline) immunogenicity value and v_{post} be the post-vaccination value, then the fold increase is

$$f_i = v_{post}/v_{pre}.$$

Fold increases express intra-individual relative increases in immunogenicity values. Just like immunogenicity values, log transformed fold increases tend to be normally distributed, and for the statistical analysis of fold increases the methods described for the analysis of immunogenicity values can be used.

13. Interim Analysis

Not applicable. Regarding summaries planned for DSMB meetings, please refer to a standalone DSMB Charter.

14. Changes in the Planned Analysis

Not applicable in this version.

15. Appendices

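### Pooling the 3:1 four-dose and 1:1 five-dose LRG cohorts without stratifying leaves cohort unbalanced between arms in the descriptive LRG RVNA and safety comparisons

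*SAP*

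**What the plan says.** SAP Section 3.1.2 sets the first allocation: "The initial 20 subjects in the LRG will be randomized on a 3:1 (SYN023 to HRIG) ratio". SAP Section 3.1.4 adds 60 subjects, for whom "Subjects in general enrollment LRG will be allocated with a 1:1 randomization to either SYN023 or HRIG treatment arms". SAP Table 4.1-1 gives the resulting counts: 15 SYN023 and 5 HRIG in the initial cohort, 30 and 30 in the general cohort.

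The vaccine schedule changes between the cohorts. SAP Section 3.3: "If a subject is enrolled under Protocol Amendment 2.0, rabies vaccinations will be administered on Study Days 1, 4, 8, and 15"; under later versions "vaccinations will be administrated on Study Days 1, 4, 8, 15 and 29". Footnote f of the LRG schedule in SAP Section 15.1.1 likewise gives the fifth vaccination to general LRG subjects only.

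SAP Section 4 then pools: "summaries will be grouped by study group (LRG and NRG) regardless the difference in dosing schedules". Its reason is "As it is unlikely that there is any clinical difference between the 4 and 5 dose regimens". SAP Section 8.2 plans LRG RVNA ratios and response rates (RVNA at or above 0.5 IU/mL) by treatment at each time point, without hypothesis tests and without any cohort term. SAP Section 9 summarises safety by risk group and treatment. SAP Section 12, which covers anti-SYN023 antibodies, takes the other course: "Immunogenicity will be summarized for initial LRG subjects, general LRG subjects and NRG subjects, separately".

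**The concern.** Randomisation protects the arm comparison within each cohort. Merging a 3:1 cohort with a 1:1 cohort and comparing crude arm summaries gives that protection up: the SYN023 arm holds proportionally more early, four-dose subjects than the HRIG arm. A difference between cohorts, whether from the fifth dose, calendar time or site mix, then appears in part as a difference between SYN023 and HRIG.

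The LRG RVNA ratio and the percentage at or above 0.5 IU/mL at each time point are stated secondary objectives (SAP Section 2.2). Protocol Section 3.4.1 adds that LRG pharmacodynamic data will help in planning SYN023 development. A distorted descriptive ratio would therefore be read and used even though it is not tested.

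**Working it through.** **Inputs.** Initial LRG: 20 subjects at 3:1. General LRG: 60 at 1:1 (SAP Sections 3.1.2 and 3.1.4, Table 4.1-1). Stated LRG total 80, with up to 45 on SYN023 (SAP Section 4.1).

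**The plan's own figure.** SYN023: 20 × 3/4 + 60/2 = 15 + 30 = 45. HRIG: 20 × 1/4 + 60/2 = 5 + 30 = 35. Total 80. These agree with the SAP.

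**Imbalance.** Share from the initial cohort: SYN023 15/45 = 33.3%, HRIG 5/35 = 14.3%. The difference is 19.0 percentage points; the odds ratio is (15 × 30)/(5 × 30) = 3.0.

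**Effect on the ratio.** Let k be the general-cohort geometric mean divided by the initial-cohort one, with the same treatment effect in both cohorts. On the log scale the initial cohort lowers the SYN023 mean by (15/45) ln k and the HRIG mean by (5/35) ln k. The pooled log ratio therefore shifts by −(0.333 − 0.143) ln k = −0.190 ln k, and the pooled ratio is multiplied by k^-0.190. The documents give no k, so the range is an assumption:

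| Factor between cohorts | General higher | Initial higher |
|---|---|---|
| 1.1 | 0.982 | 1.018 |
| 1.25 | 0.958 | 1.043 |
| 1.5 | 0.926 | 1.080 |
| 2.0 | 0.876 | 1.141 |

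**Effect on the response rate.** A 10-point difference between cohorts would shift the pooled rate difference by 0.190 × 10 = 1.9 points.

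**When schedule can act.** The two schedules are the same through Day 15, and SAP Section 11.2 has the Day 29 RVNA sample drawn before that day's vaccination. A fifth-dose effect can reach RVNA only from Day 43, which includes Day 99. At earlier visits only enrolment phase can differ. For safety, unsolicited events run to Day 43 (SAP Section 9.1); by the plan 30/45 = 66.7% of SYN023 but 30/35 = 85.7% of HRIG subjects receive a fifth dose within that period.

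**Cost of stratifying.** With a common log SD, the variance factor of the crude contrast is 1/45 + 1/35 = 0.0508. Within-cohort information is 15 × 5/20 = 3.75 (initial) and 30 × 30/60 = 15 (general), so the weights are 0.20 and 0.80 and the stratified factor is 1/18.75 = 0.0533. The variance ratio is 1.05, so the standard error rises by a factor of √1.05 = 1.025. Using the general cohort alone gives 1/30 + 1/30 = 0.0667, a standard error about 14.6% larger than the crude one.

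**The case against.** The pooling is disclosed, prespecified and given a reason, so it is not an oversight. The LRG contrasts are untested, and the primary and both tested secondary analyses use the NRG per-protocol set, where all subjects are planned for five doses. The bias may also be small against noise. The prior-trial Day 84 ratio interval of 64.04% to 122.30% (Protocol Table 7.8.2-2; 72 and 75 subjects) implies a log SD near 1.0. If the LRG is similar, 45 against 35 gives a standard error of about √0.0508 = 0.225, and the shift is about 0.19 standard errors at k = 1.25 and 0.59 at k = 2.0. If the fifth dose raises titres, the bias runs against SYN023 and does not flatter it.

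All of this stands, and it limits the importance of the point. It does not remove it. Absence of a clinical difference is asserted without data, and it would not in any case imply equal geometric means, which are what is compared. The protocol's own rationale for the five-dose regimen is to avoid analytic difficulty when data are combined.

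Two stronger readings are tempting. A reader might infer that every LRG arm comparison is confounded by schedule. It is not: anti-SYN023 results are already split by cohort, pharmacokinetics has no HRIG comparator, and RVNA through Day 29 precedes the fifth dose. A reader might also infer that a distorted ratio decides advancement to the NRG. SAP Section 3.1.5 does list Day 99 RVNA geometric mean among the data the DSMB judges, but sets no between-arm criterion. The numeric rule in Protocol Section 5.1.5.3 (at least 75% of SYN023 recipients in the protective range on Day 99) looks at one arm only. DSMB summaries follow a separate charter that is not among the documents.

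**Conclusion.** The point holds for the descriptive LRG RVNA ratios and response-rate comparisons at each visit, and for LRG adverse event comparisons after Day 29. The imbalance (33.3% against 14.3%) is certain from the planned counts; analysed counts may differ somewhat after exclusions. Whether it produces material bias is not known: there is none if the cohorts do not differ, and the pooled ratio moves by a factor of 0.98 to 0.88 for an assumed k of 1.1 to 2.0. For scale, k of about 1.65 would turn a true ratio of 0.88 into 0.80, since (0.88/0.80)^(1/0.190) = 1.65, though no LRG ratio is tested against 0.80. The NRG primary and tested secondary analyses are not affected. This is a cheap improvement to a stated secondary objective and does not threaten the trial's main conclusions.

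The schedule part rests on the SAP's account of the initial cohort. Current Protocol Table 2.3-1 lists that cohort with vaccination on Day 29 as well, while SAP Table 4.1-1 does not, and the two must be reconciled. The imbalance in enrolment cohort stands either way.

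**What to change.** In SAP Sections 4 and 8.2, state that LRG between-arm RVNA comparisons are stratified by enrolment cohort. For the geometric mean ratio, take the inverse-variance weighted average of the within-cohort log ratios (weights about 0.20 initial and 0.80 general at full enrolment). For the response rate, apply the same size-based weights as fixed values, because estimated variances vanish when all subjects respond, as all did at Day 84 in Protocol Table 7.8.3-1. Show LRG RVNA and safety summaries by cohort as supportive tables, as SAP Section 12 already does for anti-SYN023 antibodies, and label the unstratified pooled table as descriptive only.

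The cost is about 2.5% in standard error and a few extra tables. The cohort variable is not among the randomisation factors named in SAP Section 6, but the Section 12 tables need it in any case. The 15 against 5 ratio will be imprecise alone: at a log SD of 1.0 its standard error is √(1/15 + 1/5) = 0.52, a 95% interval factor of about 0.36 to 2.75. It should be read only as support for the stratified estimate. No clinical procedure changes.
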